5.8.3. Storage of samples

Blood samples will be processed into serum and PBMCs on the day of receipt at LVZ in accordance with local SOP or separated at the study site and shipped frozen to LVZ in batch. Processing of blood into serum and PBMCs will be carried out in line with local risk assessment.

Serum and PBMC samples will be aliquoted into cryotubes labelled by LVZ after preparation from blood. Labels will contain identical information to the blood tubes, but will also specify 'human serum' or 'human PBMCs' to denote the type of sample contained within the vial. Serum and PBMC vials will be numbered sequentially for each patient (e.g. S01, P01, P02) in accordance with local SOP. LVZ will only identify samples from these labels.

Once serum and PBMCs have been prepared, samples will be stored in cryoboxes below - 60°C in accordance with SOP MIG/001. PBMCs may be transferred to liquid nitrogen for long-term storage. Serum samples will be removed from the ultra-low temperature (ULT) freezer as and when they are tested and will be returned to the ULT freezer after testing.

The samples will be kept until the clinical study report has been finalised. The sponsor will inform LVZ when the clinical study report has been finalised and whether samples are to be returned to the study site or are to be destroyed at LVZ. If the sponsor does not inform the LVZ what to do with the samples then LVZ will return any remaining aliquots to the study site after the clinical study report has been finalised.

5.8.4. Shipment of samples

Samples will be shipped to LVZ by courier at ambient temperature on the day of blood being drawn, within normal working hours or separated and frozen at the study site to be shipped in batch at a later date. A schedule of sampling dates will be prepared by the study site and agreed with LVZ in advance to ensure availability of staff for sample receipt and processing. Any changes to this sampling schedule will be communicated to and agreed with LVZ in advance.

Upon receipt, the blood samples will be taken to test facility laboratories where details on the sample tubes will be checked to ensure that samples received are as expected. Any discrepancies will be recorded on the blood sample shipment form. The original forms will be filed in the RHM MED1776 study test sample file. For each shipment, PDF copies of the completed forms will be e-mailed to the Chief Investigator at the study site to document receipt. This e-mail will also state the sample numbers and volumes received, the date of receipt and the nature of any discrepancies. This e-mail will also request documented approval to proceed

with testing of this batch of blood samples, once processed into serum/PBMCs. A batch of samples will only be tested at LVZ once written approval is received from the sponsor for that batch.

6. Investigational Product

6.1. Description (also see Investigator's Brochure [IB])

6.2. Storage and handling

The vaccine will be stored at -20°C (nominal temperature).

Maintenance of the correct storage conditions will be the responsibility of the site using an appropriately qualified and monitored storage unit. Any temperature excursions or deviations from the procedures outlined below will be reportable to the Chief Investigator and Sponsor QP. Vaccine accountability, storage, shipment and handling will be in accordance with supplier and study site SOPs. All movements of the study vaccines will be documented. All study vaccines to be administered to the subjects must be stored in a temperature monitored locked freezer with no access by unauthorised personnel.

6.3. Dosage and administration of study vaccine

The dose administered will be dependent on group and cohort allocation. Please see **Section 3.3 Table 1** for more information on dosing groups and the corresponding dose allocation. Instructions for dose preparation can be found in the IMP procedures manual.

Table 5: Dose and corresponding administrations per vaccination visit (total of two visits).

Delivery method	Total DNA (mg)	Left deltoid	Right deltoid
ID (Tropis)	0.2	0.1ml x1	-
ID (Tropis)	0.4	0.1ml x1	0.1ml x1
ID (Tropis)	0.8	0.1ml x2	0.1ml x2
ID (Tropis)	1.2	0.1ml x3	0.1ml x3

6.3.1 Intradermal injections

The vaccine will be administered intradermally using the PharmaJet Tropis device in the deltoid muscle of both arms (when dose is >0.2mg). During administration of the vaccines, Advanced Life Support drugs and resuscitation equipment will be immediately available for the management of anaphylaxis. At each vaccination visit, vaccines will be allowed to thaw to room temperature and should be administered as soon as possible. Although the components of the drug product formulation are compatible and stable for at least 24 hours after thawing, the investigator is encouraged to administer the formulation as soon as possible, and not beyond 2 hrs after removal from the freezer. If not used within 2hrs, the final formulated vial must be discarded. Depending on dose and concentration, one or more vials of vaccine may be used.

The injection site will be covered with a sterile dressing and the volunteer will stay in the Southampton NIHR CRF for observation, in case of immediate adverse events. Observations will be taken 30 minutes after vaccination (+/-5 minutes) and the sterile dressing removed and injection site inspected. Observations will also be taken at 60 minutes (+15/-5 minutes) before the volunteer leaves.

Study vaccine will be administered by a study vaccine administrator – a trained and qualified study nurse, medical doctor, or otherwise qualified health care professional. The date and time of each study vaccine administration will be recorded in the eCRF.

6.4. Vaccine supply

6.5. Vaccine accountability

A drug accountability log will be kept by the investigational pharmacist or designee, in which he/she will record the date(s) and quantity of all IMP dispensed for each volunteer. The inventory will be made available to the study monitor who will verify accountability and dose during the course and/or at the end of the study. All used and unused containers will be accounted for during the study and will either be returned to the sponsor for destruction or destroyed on site if approved by the sponsor (in this case a written confirmation of destruction must be provided).

7. Safety

7.1. Safety definitions

Adverse Event (AE)

An AE is any untoward medical occurrence in a volunteer, including a dosing error, which may occur during or after administration of the vaccine and does not necessarily have a causal relationship with the intervention. An AE can therefore be any unfavourable and unintended sign (including an abnormal laboratory finding), symptom or disease temporally associated with the study intervention, whether or not considered related to the study intervention.

Adverse Reaction (AR)

An AR is any untoward or unintended response to the vaccine. This means that a causal relationship between the inoculum and an AE is at least a reasonable possibility, i.e., the relationship cannot be ruled out. All cases judged by either the reporting medical investigator or the sponsors as having a reasonable suspected causal relationship to the inoculum (i.e. possibly, probably or definitely related to the inoculum) will qualify as adverse reactions.

Unexpected Adverse Reaction (UAR)

An adverse reaction, the nature or severity of which is not consistent with the applicable information about the vaccine in the protocol, is considered as an unexpected adverse reaction.

Serious Adverse Event (SAE)

An SAE is an AE that results in any of the following outcomes, whether or not considered related to the study intervention.

- Death (i.e., results in death from any cause at any time)
- Life-threatening event (i.e., the volunteer was, in the view of the investigator, at immediate risk of death from the event that occurred). This does not include an AE that, if it occurred in a more serious form, might have caused death.
- Persistent or significant disability or incapacity (i.e. substantial disruption of one's ability to carry out normal life functions).
- Hospitalisation other than admission in the NIHR-CRF, regardless of length of stay, even if it is a precautionary measure for continued observation. Hospitalisation (including inpatient or outpatient hospitalisation for an elective procedure) for a pre-existing condition that has not worsened unexpectedly does not constitute a serious AE.
- An important medical event (that may not cause death, be life threatening, or require hospitalisation) that may, based upon appropriate medical judgment, jeopardise the volunteer and/or require medical or surgical intervention to prevent one of the outcomes listed above. Examples of such medical events include allergic reaction requiring intensive treatment in an emergency room or clinic, blood dyscrasias, or convulsions that do not result in inpatient hospitalisation.
- Congenital anomaly or birth defect.

Serious Adverse Reaction (SAR)

An adverse event that is both serious and, in the opinion of the reporting investigator or sponsor, believed to be possibly, probably or definitely due to the inoculum or any other study treatments, based on the information provided in the protocol.

Suspected Unexpected Serious Adverse Reactions (SUSARs)

A SUSAR is a SAE that thought to be possibly, probably or definitely related to the inoculum and is unexpected in nature (when assessed against the IB).

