5.5 Participant visits

5.5.1 Vaccination Visits

Following review of safety blood results and GP medical history, eligible subjects will be booked to attend a vaccination visit on Day 0. After re-checking inclusion and exclusion criteria, an abbreviated physical examination (at the investigator's discretion) and measurement of physical observations, subjects will be enrolled into a study group for vaccination. Volunteers will be enrolled into each group or subgroup sequentially. Volunteers will be informed of which group they will be enrolled into. Volunteers will not be randomised into a group in this study.

If medical status and/or physical examination suggest significant changes have occurred since screening, the Day 0 visit can be re-scheduled, or the subject excluded from the study if he/she fails to meet the inclusion and exclusion criteria. The study team will advise the volunteer prior to the dosing visit that receipt of licensed vaccines e.g. (FLU vaccine) is not permitted within the month preceding vaccination or the month following each vaccination. Should a volunteer have received a licensed vaccine in the month prior to pEVAC-PS vaccination the Day 0 visit will be rescheduled to an acceptable time-point.

Before vaccination, the investigator must check for any symptoms of an acute illness or body temperature \geq 37.5°C. In such a situation, the subject may be vaccinated at a later date within the screening window or be withdrawn at the discretion of the investigator. The vaccine will be administered as detailed in **Section 6.3** *Dosage and administration of study vaccine'*.

Following vaccine administration, subjects will be observed for a minimum of 60 minutes for the development of any acute reactions, or longer if deemed necessary.

Subjects will be provided with a subject diary, thermometer, and ruler to measure and record body temperature, solicited local and systemic AEs.

This will be repeated on Day 28 for administration of the second dose of vaccine.

If the volunteer has remained well during this observation period, they may go home and will receive a follow up telephone call the next day.

Any significant safety concerns that have arisen during the observation period will be communicated to the CI and local safety monitor. An extended period of observation will be instigated if necessary. In this unlikely event, the following procedures will be followed as a minimum:

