- The volunteer will be accompanied in the observation area by a trial nurse or study investigator. The frequency of physical observations (blood pressure, pulse, temperature) will be determined by the CI, for example hourly (+/- 15 minutes).
- The trial clinician may initiate basic treatments for vaccine related symptoms including anti-pyretic and anti-emetic medication.
- Intravenous fluid can also be given for tachycardia or hypotension of grade 2 or above or for any other reason of clinical significance according to the trial investigators judgement.

If at any point following vaccination, the CI or local safety monitor identifies any acute clinical concern requiring urgent medical intervention, an acute admission for further clinical management will be arranged.

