7.9.1. Group Holding Rules

The following holding rules will apply to all study groups. If a holding rule is activated, then further vaccinations will not occur until an internal safety review has been conducted by the LSC and it is deemed appropriate to restart dosing. All other procedures relating to safety and immunology will continue. The regulatory authority must be informed of the activation of any holding rule and a request to restart dosing with pertinent data must be submitted as a request for a substantial amendment. The internal safety review will consider:

• The relationship of the AE or SAE to the vaccine.

- The relationship of the AE or SAE to the vaccine dose, or other possible causes of the event.
- If appropriate, additional screening or laboratory testing for other volunteers to identify those who may develop similar symptoms and alterations to the current Participant Information Sheet (PIS) are discussed.
- New, relevant safety information from ongoing research programmes on the various components of the vaccine.

The Research Ethics Committee and IMP manufacturer will also be notified if a holding rule is activated or released. All vaccinated volunteers will be followed for safety until resolution or stabilisation (if determined to be chronic sequelae) of their AEs.

The group holding rules are as follows:

- One serious event considered by the investigator to be at least possibly related to the study drug
- Two serious adverse reactions considered by the investigator to be at least possible related to the study drug, irrespective of duration and whether the reactions are the same or not

These rules apply to both solicited and non-solicited adverse events as well as to laboratory adverse events.

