7.10. Local Safety Committee

A Local Safety Committee (LSC) will be appointed to provide real-time safety oversight. The LSC will review SAEs deemed possibly, probably or definitely related to study interventions. The LSC will be notified within 24 hours of the Investigators' being aware of their occurrence. The LSC has the power to place the study on hold if deemed necessary following a study intervention-related SAE. In addition to the LSC chair (LSM), there will be a minimum of two other appropriately qualified committee members. LSC membership details can be found in the *LSC Terms of Reference*. All correspondence between Investigator and LSC will be conveyed by the Investigator to the trial Sponsor.

The chair of the LSC may be contacted for advice and independent review by the Investigator or trial Sponsor in the following situations:

- Following any SAE deemed to be possibly, probably, or definitely related to a study intervention.
- Any other situation where the Investigator or trial Sponsor feels independent advice or review is important.

The study can be put on hold upon advice of the Chief Investigator, Study Sponsor, REC or Local Safety Committee, for any single event or combination of multiple events which, in their professional opinion, jeopardise the safety of the subjects or the reliability of the data. If the study is placed on hold it may only be restarted following discussion with and approval from the LSC, the REC, the trial Sponsor and Chief Investigator. If the clinical trial is halted and is unable to resume, a formal letter will be sent to the regulatory authorities by the Sponsor explaining the reasons for cessation of the study.

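### Section 7.1 exempts every NIHR-CRF admission from the hospitalisation criterion although none is scheduled, so an unplanned one for a vaccine reaction would not be automatically serious

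*Protocol*

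**What the plan says.** **Definition.** Protocol Section 7.1 makes an event serious if it results in "Hospitalisation other than admission in the NIHR-CRF, regardless of length of stay, even if it is a precautionary measure for continued observation". Nothing restricts the CRF exemption to planned stays.

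**Visit plan.** Section 6.3.1 has dosing followed by observation in that same unit: "the volunteer will stay in the Southampton NIHR CRF for observation, in case of immediate adverse events". Section 5.5.1 sets the duration: "subjects will be observed for a minimum of 60 minutes for the development of any acute reactions, or longer if deemed necessary". It then provides for same-day discharge: "If the volunteer has remained well during this observation period, they may go home". Table 2 (Section 5.2) and Table 3 (unscheduled and early termination visits) contain no admission.

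**Contingency.** If a significant concern arises during observation, Section 5.5.1 has it passed to the chief investigator and the local safety monitor, and adds: "An extended period of observation will be instigated if necessary". Basic medication is allowed, and "Intravenous fluid can also be given for tachycardia or hypotension of grade 2 or above". No upper time limit is given. Section 5.5.1 then describes a separate step, an acute admission where urgent intervention is needed, without naming the receiving unit.

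**Rules that use seriousness.** The first group holding rule in Section 7.9.1 is "One serious event considered by the investigator to be at least possibly related to the study drug". The second requires two related serious reactions. The individual stopping rule in Section 7.9.2 requires one related SAE. Section 7.10 states: "The LSC will review SAEs deemed possibly, probably or definitely related to study interventions". Sections 7.6.2 and 7.10 set a 24-hour notice to the LSC for those SAEs. In Section 7.1 a SUSAR is by definition an SAE.

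**The concern.** Exempting the research unit makes sense where a protocol schedules in-house stays, because otherwise every routine night would be an SAE. This protocol schedules none, so the clause has no routine stay to spare. The only CRF admission it can reach is one that nobody planned, and after dosing the likely cause is an acute reaction.

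The same sentence counts even a precautionary hospital stay as serious. Two participants with the same reaction and the same stay would then be classified differently according to the unit that keeps them. In a first-in-human escalation study whose pre-defined holding and stopping rules run on seriousness alone, that classification decides whether those rules are activated automatically.

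**Working it through.** There is no figure in the plan to reproduce. The check sets the definition against the visit plan and the rules.

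1. **Scheduled stays that the exemption covers.** CRF admissions in Tables 2 and 3, Section 5.5.1 and Section 6.3.1: 0. The exemption therefore has no planned stay to act on.

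2. **Where acute reactions would be seen.** All groups are vaccinated at the one Southampton CRF (Sections 3.2 and 3.4). With up to 36 participants and 2 doses each, 36 × 2 = 72 vaccinations. This is the total exposure, not a count of affected cases.

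3. **Same reaction, two locations.** Take a vaccine-related reaction that leads to an unplanned admission and meets no other SAE criterion.

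| | Admitted in the CRF | Admitted elsewhere |
|---|---|---|
| Hospitalisation criterion (7.1) | not met | met |
| Count towards first group holding rule, threshold 1 (7.9.1) | 0 | 1: rule activated |
| Count towards second group holding rule, threshold 2 (7.9.1) | 0 | 1 |
| Individual stopping rule (7.9.2) | not triggered | triggered |
| Formal 24-hour LSC notice (7.6.2, 7.10) | not required | required |
| Can be a SUSAR if unexpected (7.1, 7.6.3) | no | yes |

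4. **Is there a backstop by severity?** Sections 7.9.1 and 7.9.2 contain no trigger based on grade. A grade 3 reaction that is not classed as serious activates no pre-defined rule.

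5. **Other routes to seriousness.** The remaining outcome criteria in Section 7.1 stay in force, including life-threatening events. Events of special interest, among them severe hypersensitivity, are reported as SAEs under Section 7.4 wherever they are managed. The important-medical-event criterion also stays, but it rests on medical judgement. The gap is therefore the middle range: a reaction that leads to an unplanned CRF admission but is neither life-threatening nor of special interest.

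6. **What counts as an admission?** Section 5.5.1 places extended observation in the observation area and treats acute admission as a further step. The protocol does not say whether prolonged observation with intravenous fluid in the CRF is an admission, or whether the acute admission may be to the CRF itself.

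**The case against.** The case against is substantial, and much of it stands.

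- **Length of stay.** A reader might infer that a CRF stay is exempt however long it lasts. The sentence does not support that: the words on length and on precautionary observation qualify hospitalisation and widen the criterion. The exemption is open-ended only because it is not limited to planned stays.
- **Information reaching the committee.** A reader might also infer that the choice of bed decides whether the safety committee hears of the event. Section 5.5.1 contradicts this. Significant concerns during observation go to the chief investigator and the local safety monitor, whom Section 7.10 identifies as the LSC chair. Section 7.6.1 also makes AE data available to the LSC before each interim safety analysis. Only the formal 24-hour SAE notice is lost.
- **Dosing can still be paused.** Sections 7.9.2 and 7.10 allow a hold for any single event, and safety reviews precede each escalation. This stands, but a discretionary hold is not a pre-defined rule. The sentinel and 72-hour checks in Sections 3.1 and 3.5 themselves refer to Sections 7.9.1 and 7.9.
- **Main acute reactions are covered.** Anaphylaxis is captured by Section 7.4, and the important-medical-event text gives an allergic reaction treated intensively without admission as an example. This narrows the gap to the middle range but does not close it.
- **Extended observation may not be an admission.** This is correct, and it means that deleting the exemption alone might not settle the situation in Section 5.5.1. It is a reason to state the classification explicitly.

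**Conclusion.** The point holds in a limited form. The exemption in Section 7.1 is not restricted to scheduled stays, and there are 0 scheduled stays for it to cover. Its only possible effect is to take an unplanned CRF admission out of the automatic hospitalisation criterion. For a related reaction in the middle range, this changes the count towards the first group holding rule from 1 to 0, and 1 is the threshold.

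The conclusion rests on two assumptions: that a stay in the CRF can amount to an admission, which the definition itself presupposes, and that the investigator does not class the event as medically important.

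The documents do not support saying that such an event can never be an SAE or can never lead to a hold. Nor do they support saying that the SAE count is understated: that would need such a stay to occur and to escape every other criterion, and the protocol gives no rate for either. This is a definition worth correcting before dosing, not evidence that safety oversight is absent.

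**What to change.** In Section 7.1, limit the exemption to stays scheduled by the protocol (currently none) or remove it. Reconcile Section 7.1 with Sections 5.5.1 and 7.9 by stating whether extended observation in the CRF, and an acute admission to the CRF, count as hospitalisation. The sponsor should decide where observation ends and admission begins; what matters is that the boundary is written down before the first dose. The change concerns how events are classified and leaves the wording of the holding and stopping rules and the care given to participants as they are.

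The cost is a sentence or two in Section 7.1 and matching guidance on the SAE form. The downside is an occasional extra SAE report, and possibly a hold review, after a stay that proves purely precautionary. Under Section 7.9.1 an activated hold also means informing the regulator and requesting a restart as a substantial amendment, so the boundary should be chosen with that in mind.
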